Velacur offers the ability to simultaneously and noninvasively measure Attenuation Coefficient Estimate (ACE) as a quantitative measure of ultrasound attenuation¹³ and detection of hepatic steatosis in addition to LSM which measures deep volumetric liver elasticity using steady state shear waves, known as shear wave absolute viboelastography (SWAVE). This technology enables measurements of liver elasticity to a depth equal to the B-mode image, or in excess of 15 cm. The system consists of an ultrasound machine, a vibration device to excite shear waves in the patient and a ultrasound transducer. The vibration device induces shear waves in the liver at four different frequencies between 40Hz and 70Hz simultaneously. The ultrasound volume is acquired through the ribs at the same location as a typical transient elastography (TE) measurement. Volumes are collected in a fan of approximately 15 degrees and taken at a depth of 15cm, which much deeper than FibroScan® measurement (6 cm), and allows for much larger sample measurement (100,000 mm³) versus that measured by Fibroscan (3,140 mm^3).

Rationale and Specific Aims

Hypothesis and Specific Aims: *Velacur* with ACE and LSM measurements is a novel ultrasonic device that can estimate both liver steatosis and fibrosis using a sophisticated process. The availability of *Velacur* would allow a health care provider to make a diagnosis of NAFLD with or without advanced fibrosis quickly without a need for liver biopsy.

Hypothesis: The diagnosis and severity of NAFLD with or without advanced fibrosis can be defined using *Velacur*.

Specific Aims: To prospectively evaluate the utility of *Velacur* in assessing NAFLD with or without advanced fibrosis in patients seen in liver clinics for suspected NAFLD diagnosis.

Specific Aim #1: To prospectively evaluate the performance of *Velacur* for detecting hepatic steatosis and fibrosis in patients with suspected NAFLD by assessing correlation of ACE and LSM measured by *Velacur* to grade of steatosis and stage of fibrosis on liver histology of patients with NAFLD who undergo standard of care liver biopsy.

Specific Aim #2: To compare the performance of *Velacur* to that of FibroScan® in the same patient population to determine if either test is more accurate in correlating with NAFLD histology.

July 8, 2021

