Specific Aim #3: To compare the performance of *Velacur* to that of non-invasive blood based markers such as APRI, FIB4, and NAFLD fibrosis score in predicting advanced fibrosis in biopsy proven NAFLD.

Proposed Study Design: The proposed study will evaluate the performance characteristics of LSM as a measure of fibrosis and ACE as a measure of hepatic steatosis by *Velacur* in patients with different stages of NAFLD. In addition, we will compare the diagnostic accuracy of ACE to CAP and LSM measured by *Velacur* to that measured by FibroScan® using liver histology as the reference standard. We will also compare the performance of these two methods to that of non-invasive blood based markers such as APRI, FIB4, and NAFLD fibrosis score in predicting advanced fibrosis in biopsy proven NAFLD.

Inclusion/Exclusion Criteria

Inclusion criteria:

- 1. Adults aged 18 years or older
- 2. History of biopsy proven NAFLD or NASH within 6 months prior to enrollment
- 3. Planned liver biopsy for evaluation of NAFLD within 6 months of enrollment
- 4. Suspected NAFLD or NASH with planned or recommended standard of care liver biopsy
- 5. Ability to provide informed consent

Exclusion criteria:

- 1. Fasting for less than three hours prior to the scan
- 2. Subject is a pregnant or lactating female
- 3. Subject with current, significant alcohol consumption or history of significant alcohol consumption for a period of more than 3 consecutive months any time within 1 year prior to screening. Significant alcohol consumption is defined as more than 20 gram per day in females and more than 30 grams per day in males, on average (a standard drink in the US is considered to be 14 grams of alcohol).
- 4. Subject is unable to reliably quantify alcohol consumption based upon local study physician judgment.
- 5. Subject uses drugs historically associated with NAFLD (amiodarone, methotrexate, systemic glucocorticoids, tetracyclines, tamoxifen, estrogens at doses greater than those used for hormone replacement, anabolic steroids, valproic acid, and other known hepatotoxins) for more than 2 weeks in the year prior to screening
- 6. Subject with history of cirrhosis and clinical evidence of hepatic decompensation as defined by the presence of any of the following abnormalities at screening:
 - a. Serum albumin less than 3.5 grams/deciliter (g/dL).
 - b. An INR greater than 1.5.
 - c. Total bilirubin greater than 2 milligrams per deciliter (mg/dL).

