Participation in this study may cause a loss of privacy. To minimize this risk, all of the patient's personal and medical data will be considered confidential to the extent allowed by law; every effort will be made to keep all of the information strictly confidential. All study information will be stored in locked cabinets and on password-protected computers. Only authorized personnel will have access to the samples, databases, and results. Samples will be labeled with a code. When the study is published, no names or other identifying information will be used.

While there are no direct risks from use of *Velacur*, patients may be uncomfortable lying on their back for a brief period of time. They may experience soreness at the probe site. There is a small risk of an allergic reaction to the gel utilized during the procedure.

Patients will be closely monitored for any evidence of adverse events. Any adverse events associated with the study will be documented and the IRB will be notified per reporting guidelines.

Given this is a minimal risk study, no Data Safety and Monitoring Board (DSMB) will be required.

Study Withdrawal/Discontinuation

Participants are free to withdraw from the study for any reason and at any time without giving a reason for doing so and without penalty or prejudice. The Investigator is also free to terminate a subject's involvement in the study at any time if the subject's clinical condition warrants it.

Statistical Considerations

Descriptive statistics such as mean, standard error, and percentages were used to characterize the cohort. Comparisons will be made between groups by using Student t test or analysis of variance. Pearson correlation coefficient will be used to detect the correlation between continuous variables. Multivariate analysis will be performed to examine the independent association between dependent and several independent variables. Sample size is based on clinical experience and precedent established for studies of similar design.

Privacy/Confidentiality Issues

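### The planned methods give Aim 2 no inference on Velacur versus FibroScan, and give Aim 3 neither an accuracy measure nor a comparison with the blood markers

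*Protocol*

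**What the plan says.** Specific Aim #2 sets Velacur against FibroScan "in the same patient population to determine if either test is more accurate in correlating with NAFLD histology". Proposed Study Design goes further: "we will compare the diagnostic accuracy of ACE to CAP and LSM measured by" Velacur to the FibroScan value, "using liver histology as the reference standard". It continues: "We will also compare the performance of these two methods to that of non-invasive blood based markers", with advanced fibrosis as the target, which is also the target of Specific Aim #3. Specific Aim #1 relates ACE and LSM "to grade of steatosis and stage of fibrosis on liver histology of patients with NAFLD".

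After descriptive statistics, the protocol's Statistical Considerations section names three methods:

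- For differences in means, with the groups left undefined: "Comparisons will be made between groups by using Student t test or analysis of variance"
- For association, with no method for setting one coefficient against another: "Pearson correlation coefficient will be used to detect the correlation between continuous variables"
- For a model whose outcome and covariates are not named: "Multivariate analysis will be performed to examine the independent association between dependent and several independent variables"

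The SAP repeats the paragraph unchanged. It names no AUROC, sensitivity, specificity or cut-off, no paired test, and no confidence interval for a difference between tests. It mentions neither FibroScan nor any blood marker.

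Neither document defines advanced fibrosis by stage. Study Procedures provides a central pathologist's read on the NASH CRN system and a separate artificial-intelligence read, and also collects clinical biopsy results from the records. It does not say which read is the reference.

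**The concern.** Aims 2 and 3 ask how well several tests, all applied to the same patients, agree with one reference, and which does so better. The listed methods answer other questions: whether a marker's mean differs between groups, whether two continuous quantities are linearly related, and whether a variable is independently associated with an unnamed outcome.

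Followed as written, the study could report which device has the larger correlation with histology, but not whether the gap exceeds chance. It would give no estimate of how well any test identifies advanced fibrosis. The accuracy measure, histological target, reference read and method of comparison are all left open, so they could be chosen once results are visible.

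**Working it through.** **Aims against methods**

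| Planned method | What it gives | What Aims 2 and 3 need |
|---|---|---|
| t test / ANOVA | Whether one marker's mean differs between histology groups | Whether two markers differ in accuracy in the same patients |
| Pearson | One coefficient per device; usable as a ranking for Aim 2 | A CI or test for the difference between two dependent correlations; grade and stage are ordinal, while Pearson is specified for continuous variables |
| Multivariate analysis | Independent association; outcome and covariates unnamed | Accuracy for a binary target, compared between tests |

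The finding rests on this table. The figures below show only how much it matters.

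**Inputs.** N = 100 is the protocol's upper limit (Enrollment/Randomization). It rests on experience and precedent, so there is no calculation to reproduce. Everything else is assumed: normally distributed markers; correlation between the two markers within disease group of 0.4 to 0.8; 20% to 40% with advanced fibrosis; and 60 usable pairs as an example of missing comparator results.

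**Group t tests.** An AUROC A corresponds to a standardised mean difference d′ = √2·Φ⁻¹(A). For 0.85, d′ = 1.414 × 1.036 = 1.466. For 0.75, d′ = 1.414 × 0.674 = 0.954. Approximate power is Φ(d′·√(n₁n₀/N) − 1.96). With 20 advanced and 80 not, √(20 × 80/100) = 4:

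- AUROC 0.85: Φ(5.86 − 1.96), effectively 100%.
- AUROC 0.75: Φ(3.82 − 1.96) = Φ(1.86), about 97%.

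Both tests are therefore usually significant whether or not their accuracy is equal. Simulation over the assumed ranges (4,000 trials per scenario; extremes for 0.85 vs 0.85, 0.80 and 0.75 repeated with 20,000) gives:

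| AUROCs | Both t tests significant, N = 100 | 60 pairs | Paired DeLong rejects, N = 100 | 60 pairs |
|---|---|---|---|---|
| 0.85 vs 0.85 | about 100% | 99–100% | about 4–5% | about 4–5% |
| 0.85 vs 0.80 | not shown | not shown | 14–38% | 10–22% |
| 0.85 vs 0.75 | 96.5% to over 99% | 82–95% | 36–89% | 24–65% |
| 0.85 vs 0.65 | 57–75% | 37–54% | not shown | not shown |

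The t-test pattern starts to separate the markers only when the comparator is much weaker. For 0.85 vs 0.75 the DeLong 95% CI half-width is 0.065 to 0.122 at N = 100 and 0.086 to 0.158 with 60 pairs.

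**Closed-form check of the paired AUROC power.** Hanley–McNeil variance: V(A) = [A(1−A) + (n₁−1)(Q₁−A²) + (n₀−1)(Q₂−A²)]/(n₁n₀), with Q₁ = A/(2−A) and Q₂ = 2A²/(1+A). With 30 advanced and 70 not, the SE is 0.0471 for A = 0.85 and 0.0570 for A = 0.75. With correlation 0.5 between the two AUROC estimates (not the same quantity as the marker correlation above):

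- SE of the difference = √(0.0471² + 0.0570² − 2 × 0.5 × 0.0471 × 0.0570) = 0.0527.
- Power = Φ(0.10/0.0527 − 1.96) = Φ(−0.06), about 47%.

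Over 20% to 50% with advanced fibrosis and correlation 0.3 to 0.7 between the estimates, power is 27% to 81% for 0.85 vs 0.75 and 11% to 33% for 0.85 vs 0.80.

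**Pearson with fibrosis stage.** Assumed shares for stages 0 to 4 are 20/25/25/20/10%, with a linear shift per stage set to give the stated AUROC for stage 3 or higher (3,000 trials). Mean r is 0.67, 0.58 and 0.48 for AUROC 0.85, 0.80 and 0.75.

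- The better marker has the larger r at 0.85 vs 0.75 in over 99% of trials (N = 100) and 98% to over 99% (N = 60). At 0.85 vs 0.80 this is 93% to 99% and 87% to 97%.
- Two equal markers (0.85) also yield a winner, 50/50. At correlations 0.4, 0.6 and 0.8, 95% of chance gaps in r lie within ±0.11, ±0.09 and ±0.07 (N = 100), or ±0.15, ±0.12 and ±0.09 (N = 60).
- The average gap for 0.85 vs 0.80 is 0.67 − 0.58 = 0.09. That is inside the chance range at correlation 0.4 with N = 100, and at 0.4 to 0.6 with N = 60.

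**A CI for the difference in rank correlation.** A paired percentile bootstrap for Spearman's coefficient under the same model, at correlations 0.4 and 0.8 (800 trials, 400 resamples, so less precise), excludes zero in 4% to 5% of trials at equality. At 0.85 vs 0.75 it does so in 71% to 98% (N = 100) and 46% to 87% (N = 60).

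**The case against.** The best reply is that Aim 2 is itself worded as correlation with histology, so Pearson is a relevant measure and putting AUROC first is partly preference. The simulation supports some of this. Pearson applied to stage ranks unequal markers well, so the ordinal scale is not shown to do harm, and the CI for a correlation difference excluded zero at least as often as DeLong did (the two models make different prevalence assumptions). What stands is that a CI for the difference in correlations would be the smallest repair for Aim 2's own wording. But Proposed Study Design also promises diagnostic accuracy, and no interval or test for a difference is planned on either scale.

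For Aim 3, a multivariate model could hold Velacur LSM and the blood markers together. The text does not exclude this, but it names no variables, and independent association would still not measure accuracy.

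It is also fair that the documents show only that these choices are unrecorded, not that they would be made late; that the AI read is nowhere called a reference; and that all magnitudes depend on assumed inputs. None of this supplies the missing method.

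**Conclusion.** The concern holds and should be fixed before analysis. Two of the three aims lack a stated method that answers them: Aim 2 has a possible ranking without inference, and Aim 3 has neither an accuracy measure nor a comparison. This follows from the text and does not depend on the simulations.

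Under the assumed inputs, group t tests barely distinguish equal accuracy from an AUROC gap of 0.10 at N = 100, and an unqualified ranking by correlation cannot be told from chance when the true gap is modest. A paired comparison resolves this only partly: with up to 100 patients a gap of 0.10 may be missed, and one of 0.05 usually would be.

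**What to change.** For Aims 2 and 3, replace the t test/ANOVA sentence with text such as:

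> For each test, AUROC with 95% CI will be estimated against the central NASH CRN pathologist read. Tests will be compared by the paired difference in AUROC (for example DeLong) with 95% CI in patients who have both results: Velacur LSM vs FibroScan LSM for advanced fibrosis; ACE vs CAP for steatosis; and each device's LSM vs APRI, FIB4 and NAFLD fibrosis score for advanced fibrosis.

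In addition:

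- State, before analysis, the fibrosis stage and steatosis grade that define the targets. The documents define neither, and the choice is the sponsor's.
- State the role of the AI read, for example a sensitivity analysis. Naming the central read as reference also settles the status of the local biopsy report.
- For the correlations in Aims 1 and 2, use a rank correlation with grade or stage. For Aim 2, give a paired bootstrap 95% CI for the difference.
- The text yields 1 + 1 + 2 × 3 = 8 paired comparisons. Any ranking among them is the sponsor's choice and should be written down.
- For each comparison, report how many patients lack a comparator result, and state that a non-significant difference is not evidence of equal accuracy.
- Keep the t test and ANOVA for description.

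The cost is SAP wording and a little more analysis, with no new study procedure. The drawback is precision. Study Procedures takes laboratory and imaging results from routine records and does not list FibroScan as a study procedure, so the paired comparisons may use fewer than 100 patients.

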Study title: Quantitative Ultrasound with Velacur for Evaluation of Non-Alcoholic Fatty Liver Disease

PI: [name] MD

NCT 04576923

Document date: July 8, 2021

July 8, 2021

Quantitative Ultrasound with Velacur for Evaluation of Non-Alcoholic Fatty Liver Disease

Background

Nonalcoholic fatty liver disease (NAFLD) is the most common liver disease worldwide ¹. It is characterized by increased hepatic fat accumulation in the absence of significant alcohol intake. NAFLD has a wide spectrum that starts with simple accumulation of triglycerides droplets in hepatocytes (macrosteatosis) without associated inflammation, hepatocyte injury or fibrosis, a phenotype called non-alcoholic fatty liver (NAFL) ². A more severe NAFLD phenotype is nonalcoholic steatohepatitis (NASH), which in addition to the presence of macrosteatosis is characterized by hepatocyte ballooning, lobular inflammation with or without fibrosis. While NAFL generally has a benign course, NASH may progress to cause cirrhosis, liver failure and hepatocellular carcinoma (HCC) ^{3, 4}.

The global prevalence of NAFLD in the general population is estimated at 25% and it increases with age ¹. There is geographic variation in NAFLD prevalence probably due to differences in populations' genetic compositions, dietary habits and environmental aspects. About a quarter of the populations in Europe and North America are estimated to have NAFLD, whereas populations in South America and the Middle East are estimated to have the highest rates of NAFLD globally (range 30-32%)¹. NASH is estimated to affect 2% - 6% .of the general population, 7% - 30% of NAFLD patients who had a liver biopsy without a specific clinical indication (e.g. evaluation for liver organ donation), and 59% in NAFLD patients with clinical indication for liver biopsy (e.g. elevated liver enzymes) ¹.

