 - d. please note that people with compensated cirrhosis are not excluded from the study protocol
- 7. Subject has a history of bleeding esophageal varices, ascites or hepatic encephalopathy
- 8. Subject has history of other forms of chronic liver diseases such as viral hepatitis, autoimmune hepatitis, cholestatic liver disease (primary biliary cirrhosis or primary sclerosing cholangitis).
- 9. Subject with active substance abuse
- 10. Acute hepatitis defined as AST/ALT > 500 U/L
- 11. Patients with a pacemaker or defibrillator

12. Ascites

Enrollment/Randomization

Up to 100 patients will be seen at 3 different sites: Indiana University, Arizona Liver Institute, and Cedars-Sinai Medical Center.

Study Procedures

All patients have to be fasting for 3 hours prior to performance of the study. After subject identification and informed consent, measurement of liver stiffness with *Velacur* will be performed by a certified technician. At that time, subject participation in the protocol is complete. Duration of participation for the subject should be no more than one hour. Medical information from the subjects, including results of the laboratory and imaging tests, liver biopsy results and medical history will be collected from medical records and entered into a database. None of these tests would have been performed as part of this study, rather of as part of routine clinical care the patient receives. Laboratory data to calculate non-invasive blood based markers such as APRI, FIB4, and NAFLD fibrosis score generated within 6 months of the date of the liver biopsy will be collected. Additionally, slides from a standard of care liver biopsy will be made from the tissue collected during the biopsy and will be read centrally according to the NASH CRN system by an experienced pathologist. Digital slides will be created and read via artificial intelligence and the results of the readings will be added to the study database.

Reporting of Adverse Events or Unanticipated Problems Involving Risk to Participants or Others

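### Only equal-variance group tests are named, for undefined groups whose sizes nothing controls; if spread differs by stage, the 5% error rate is wrong in a direction the documents do not settle (minor).

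*Protocol*

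**What the plan says.** The Statistical Considerations section of the protocol, repeated word for word in the SAP, gives one sentence on group comparisons: "Comparisons will be made between groups by using Student t test or analysis of variance". It names no Welch, rank-based or transformed alternative and no check of variances. It does not say which groups are compared, on which measurement, or at what significance level.

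The rest of the protocol gives some context:

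- **Groups.** There are no randomised arms. Specific Aim #1 is pursued by "assessing correlation of ACE and LSM measured by *Velacur* to grade of steatosis and stage of fibrosis on liver histology", and Specific Aim #3 concerns advanced fibrosis. Steatosis grade, fibrosis stage and advanced versus non-advanced fibrosis are therefore the natural groups, but this is an inference.
- **Sizes.** The enrolment section says "Up to 100 patients will be seen at 3 different sites". The study design refers to performance "in patients with different stages of NAFLD", but sets no quota, stratification or expected stage distribution. On the total, the plan says "Sample size is based on clinical experience and precedent established for studies of similar design".
- **Spread.** No SD of liver stiffness (LSM) or attenuation (ACE) is given, overall or by stage. The exclusion criteria add "please note that people with compensated cirrhosis are not excluded from the study protocol", so a wide range of stiffness is plausible.

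**The concern.** Student's t test and ordinary analysis of variance pool the within-group variances into one estimate. The pooled value is weighted towards the larger group, whereas the true variance of a difference in means is driven most by the smaller group. When sizes and variances both differ, the standard error is wrong, and so is the p-value.

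Both conditions are plausible here. Biopsy decides the split and nothing balances it. Stiffness may well vary more among patients with more fibrosis, particularly as compensated cirrhosis is admitted. At stake is the calibration of the only group tests the plan names: they could declare differences too readily, or miss real ones.

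**Working it through.** The plan states no alpha, power, effect size or SD, so it has no figure of its own to reproduce. The check asks how far the named tests depart from 5%.

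**Inputs.** Total N = 100 is the protocol's maximum. Assumed: two-sided 5% level, normal data, SD of 1 in the less variable group and *r* in the more variable group (*r* = 1.5, 2, 3), and 20 to 70 of the 100 patients in the more variable group.

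**Formula.** Let n₂ be the size of the more variable group and n₁ = 100 − n₂.

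- Variance the test uses: V_pooled = [(n₁ − 1) + (n₂ − 1)r²]/98 × (1/n₁ + 1/n₂)
- True variance: V_true = 1/n₁ + r²/n₂
- Large-sample type I error: 2 × [1 − Φ(1.96 × √(V_pooled/V_true))]

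**More variable group smaller (n₂ = 30, r = 2).** V_pooled = (69 + 29 × 4)/98 × (1/70 + 1/30) = 1.888 × 0.0476 = 0.0899. V_true = 1/70 + 4/30 = 0.1476. The ratio is 0.609 and 1.96 × √0.609 = 1.53, so the error is 12.6%.

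**More variable group larger (n₂ = 70, r = 2).** V_pooled = (29 + 69 × 4)/98 × 0.0476 = 3.112 × 0.0476 = 0.1482. V_true = 1/30 + 4/70 = 0.0905. The ratio is 1.638 and 1.96 × √1.638 = 2.51, so the error is 1.2%.

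**Simulation of Student's t test** (equal means, 100,000 data sets per setting, Monte Carlo standard error about 0.07 points):

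| More variable group, of 100 | r = 1.5 | r = 2 | r = 3 |
|---|---|---|---|
| 20 | 12.2% | 18.1% | 25.3% |
| 30 | 9.3% | 12.6% | 16.4% |
| 40 | 7.0% | 8.4% | 9.7% |
| 50 | 5.1% | 5.0% | 5.2% |
| 60 | 3.4% | 2.8% | 2.2% |
| 70 | 2.2% | 1.3% | 0.7% |

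Welch's t test stays between 4.8% and 5.1% throughout. With equal variances both tests are at about 5%.

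**Power when the more variable group is the larger (n₂ = 70).** Take a true difference of 2.8 × √V_true, for which Welch's test has about 79% power. The large-sample power of Student's test is Φ(2.8 − 1.96 × √(V_pooled/V_true)):

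- r = 1.5: Φ(2.8 − 2.292) = 69%
- r = 2: Φ(2.8 − 2.508) = 61%
- r = 3: Φ(2.8 − 2.738) = 52%

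Simulation agrees to within about a point.

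**Five-group analysis of variance** (50,000 data sets per setting, SD rising evenly across groups):

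| Group sizes, least to most variable | SD 1 to 2 | SD 1 to 3 |
|---|---|---|
| 30, 25, 20, 15, 10 | 11.0% | 15.0% |
| 20 each | 5.8% | 6.6% |
| 10, 15, 20, 25, 30 | 2.9% | 2.8% |

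Welch's analysis of variance stays at 5.0% to 5.3%.

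**The case against.** The strongest objection is that a reader might infer more than the documents support. Four such readings need limiting.

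1. **That the p-values are too small whenever spread rises with fibrosis.** This does not follow. It also requires the more variable group to be the smaller one; with balanced groups Student's test is sound, and with the reverse imbalance it is conservative. The documents do not say that advanced fibrosis will be the minority. Patients enter with a biopsy done, planned or recommended, and compensated cirrhosis is admitted. The only background figure for clinically indicated biopsy is 59% with NASH. That is not a fibrosis figure, but it shows that the more diseased group need not be the smaller one.
2. **That the plan specifies pooled tests for unequal histology groups.** It says only that groups will be compared. Histology groups, unequal sizes and the pooled form of the t test are natural readings, not stated facts.
3. **That confidence intervals for group differences will be too narrow.** The statistical section plans no such intervals.
4. **That the aims are compromised.** None of them is mainly a test of equal means. They concern correlation with histology and comparative accuracy against FibroScan and blood markers, and a better group test would not supply an accuracy analysis.

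All four limits stand. They do not remove the point. The named tests are reliable only if group sizes or variances are about equal, and the plan secures neither. The conservative case is not harmless either, because it costs power.

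**Conclusion.** The point holds as a minor one. The plan names only equal-variance tests for groups it does not define and whose sizes it does not control. If spread differs by stage, the real error rate could lie well above or well below 5%, and the documents do not allow either its direction or its size to be fixed. Over the settings tabulated for the t test it runs from about 25% (20 of 100 in the more variable group, SD ratio 3) to 0.7% (70 of 100, same ratio), with no material error at 50 versus 50. Every group size, SD ratio and significance level used is an assumption, as is normality. The effect on the study's conclusions is secondary.

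**What to change.** Replace the sentence in both documents with:

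> Two-group comparisons will use Welch's t test and comparisons of more than two groups will use Welch's analysis of variance; groups are defined by central histology (steatosis grade, fibrosis stage, advanced versus non-advanced fibrosis).

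The central reading already planned under Study Procedures supplies the groups, so no new data are needed. The definition should also state which stages count as advanced, since the aims use the term without a cut-off. A log transformation or a trend test is not needed to cure this problem.

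The cost is a small loss of power if variances are in fact equal: in simulation, 77.3% for Welch against 79.4% for Student at 20 versus 80 (2.1 points), and 78.6% against 79.2% at 30 versus 70 (0.6 points).
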